### 8.5 Statistical Analysis

All patients who received any MSC infusions in the MSCs arm or supportive care in the control arm will be included in the safety analyses. All efficacy analysis will be based on the intent to treat (ITT) population, defined as eligible and randomized subjects.

Adverse event data and corresponding toxicity grades after treatment will be summarized descriptively by treatment arms. All adverse events, grades, and attributions

will be listed and tabulated. Toxicity information including the type, severity, time of onset, time of resolution, and the probable association with the study regimen will be tabulated and summarized by treatment arms. Rate of tSAEs in patients treated with MSCs will be reported as proportion and its 95% confidence interval overall and by cancer status (cancer patients versus non-oncologic patients).

Clinical outcome data (increase in oxygen saturation, decrease in oxygen supplementation, progression to mechanical ventilation or ECMO, evolution of other end-organ damage, severity of ARDS, mortality rate, cause of death, duration on ventilation, durations of ICU stay and hospital stay, duration of vasopressor use, negative SARS-Co-V-2 RT-PCR by day 28, and change in disease severity scores and corticosteroid use) will be summarized descriptively. Categorical variables will be summarized by frequencies and percentages. Continuous variables will be summarized by means, standard deviations, medians, interquartile ranges.

Proportion of patients who have an improvement of at least two categories on a six category ordinal scale at day 14 and day 28 will be summarized using rate and their 95% confidence interval by treatment arms and compared with Chi-square tests. Proportion of patients with improvement will also be reported by cancer status. As exploratory analyses, improvement in clinical status will also be assessed using logistic regression, adjusting for potential confounders such as age, race/ethnicity, underlying condition, and severity of ARDS. Changes in the six-point ordinal scale, oxygen saturation, required FiO2, severity scores from baseline will be presented graphically and compared with paired t-tests or Wilcoxon signed rank tests, whichever are appropriate (comparisons are considered exploratory). Duration of overall survival will be days from date of randomization to date of death or date of last follow-up for censoring. Overall survival will be calculated using Kaplan-Meier survival curves with estimates of medians and 95% confidence intervals by each treatment arm and compared with a log-rank test (comparison is considered exploratory).

Laboratory data, which include inflammatory markers and chest imaging will be reported with appropriate summary statistics. Changes from baseline to post-treatment will be plotted for each patient over time and assessed using paired test methodologies when appropriate. Comparison between the two treatment groups will be exploratory with appropriate two-sample tests.

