### **2.3.2 Secondary endpoints:**

1. Clinical status at day 28 as determined by 6-point ordinal scale
2. Severity of ARDS at day 14
3. Oxygenation free days at day 28
4. Progression to mechanical ventilation or ECMO
5. Duration of mechanical ventilation and/or ECMO (ventilation/ECMO free days at day 28)
6. Duration of ICU stay (ICU free days at day 28)
7. Duration of hospital stay (time to discharge)
8. Overall survival
9. All-cause mortality at day 28

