### **8.2 Sample size**

This early phase study will accrue a total of 66 patients with 6 patients for safety run in and additional 30 patients in each treatment arm by randomization. MSCs will be manufactured in our GMP facility and available to treat at least 36 patients. The study primary efficacy endpoint is improvement in clinical status at least two categories on a six-category ordinal scale at day 14 post randomization. The six-category ordinal scale ranges from 6 to 1 with a higher score indicates worse clinical outcome, i.e. 6 = death; 5 = hospitalization, requiring ECMO and/or IMV; 4 = hospitalization, requiring NIV and/or HFNC therapy; 3 = hospitalization, requiring supplemental oxygen (but not NIV/HFNC); 2 = hospitalization, not requiring supplemental oxygen; 1 = hospital discharge. The scale will be used to evaluate patients' status daily from baseline to day hospital discharge. Patients' clinical status at day 14 post randomization will be dichotomized as 'improved' (decreased by at least two categories) or 'not improved'. Patients who died before day 14 will be deemed as 'not improved'. Public data about the novel COVID-19 are limited and the data varies between all studies. Based on reported data, the time to improvement in patients with supportive care were about 22-23 days [20, 82] we expect 10% patients in the control group and 35%

patients in the MSC group will achieve 'improved' status at day 14, a total sample size of 66 (36 in the MSC arm and 30 in the control arm) will provide 84% power to detect a difference in clinical improvement of 25% between control (10%) and MSC (35%) at a 7.5% one-sided significance level using a Chi-square test.

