### 8.3 Randomization and Stratification

After safety run in, patients will be randomized in a 1:1 ratio to receive either MSCs or supportive care. Randomization will be stratified by severity of ARDS (moderate and severe), and employ permuted blocks method.

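### The primary Chi-square test ignores the ARDS-severity strata used in randomization (conservative, small power cost), and the exploratory paired tests of change do not compare MSC with control

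*Combined protocol and SAP*

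**What the plan says.** Section 8.3 of the combined protocol and SAP states: "Randomization will be stratified by severity of ARDS (moderate and severe), and employ permuted blocks method". Section 5.2 says the same.

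Section 8.5 sets the comparison of two-category improvement at days 14 and 28: the proportions "will be summarized using rate and their 95% confidence interval by treatment arms and compared with Chi-square tests". No stratification is mentioned. Section 8.2 powers the trial on the same test, "at a 7.5% one-sided significance level using a Chi-square test". ARDS severity appears in section 8.5 only as one of several covariates in a logistic regression that is labelled exploratory.

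For changes from baseline in the six-point scale, oxygen saturation, required FiO2 and severity scores, section 8.5 says that they will be "presented graphically and compared with paired t-tests or Wilcoxon signed rank tests", and labels these comparisons exploratory. The next paragraph, on laboratory data and imaging, ends by saying that the two treatment groups will be compared, also as exploratory, by suitable two-sample tests. It names no test and does not say whether it reaches back to the scale and oxygenation measures.

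The first secondary endpoint in section 2.3.2 is "Clinical status at day 28 as determined by 6-point ordinal scale". Its only stated between-arm comparison is the dichotomy, improved by two categories or not.

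**The concern.** When patients are randomized within strata of a prognostic factor, the arms are balanced on it, and the difference between arms varies less than an unstratified test assumes. The test then runs below its nominal level and gives up some power. The protocol treats severity as prognostic: section 1.1 links more severe ARDS to higher mortality, and section 1.3 lists disease severity as a risk factor. With only 30 randomized patients per arm, there is little reason to give power away.

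The paired tests have a different problem. The study objective is MSC versus control. A paired t-test or signed-rank test asks whether patients changed from baseline, and that question does not involve the other arm. Patients enter with PaO2/FiO2 of 200 mmHg or less, so survivors tend to improve whatever they receive. In an open-label trial, a small p-value for change among MSC patients is easily read as benefit.

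**Working it through.** **1. The plan's own power figure.** Inputs from section 8.2: "a total sample size of 66 (36 in the MSC arm and 30 in the control arm", 10% v 35%, one-sided 7.5% (z = 1.4395), stated power 84%.

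Power = Φ[(d − z·SE0)/SE1], where SE0 uses the pooled proportion and SE1 the separate ones.

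- Pooled p = (30×0.10 + 36×0.35)/66 = 15.6/66 = 0.236
- SE0 = √[0.236×0.764×(1/30 + 1/36)] = 0.1050
- SE1 = √[0.09/30 + 0.2275/36] = 0.0965
- Power = Φ[(0.25 − 1.4395×0.1050)/0.0965] = Φ(1.02) = 84.7%

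This reproduces the plan's figure. The 36 includes six run-in patients who are not randomized, while the ITT population is randomized patients only. For 30 v 30 the same formula gives 82.2% (exact enumeration 83.6%). The comparisons below use 30 v 30.

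**2. Why leaving out the strata is conservative.** With strata balanced between arms, the null variance of the difference is proportional to the average of p(1−p) within strata. The unstratified test uses p(1−p) at the overall rate, which is larger. Two assumed examples, strata 50:50:

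- Moderate 17%, severe 3%: overall 0.10×0.90 = 0.0900; within strata (0.1411 + 0.0291)/2 = 0.0851. Effective critical value 1.4395×√(0.0900/0.0851) = 1.480, size about 6.9%.
- Moderate 60%, severe 10%: overall 0.35×0.65 = 0.2275; within strata (0.24 + 0.09)/2 = 0.165. Effective critical value 1.4395×√(0.2275/0.165) = 1.690, size about 4.6%.

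Simulation gives 6.4% and about 4.2%. Discreteness of the counts takes the rest.

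**3. Unstratified Chi-square v CMH at the planned rates.** The documents give neither the moderate/severe split nor the effect of severity on improvement. Assumed: splits of 20/10, 15/15 and 10/20 per arm, and severity odds ratios (severe v moderate) from 1 to 0.1. Overall rates were held at 10% and 35%, with 200,000 trials per scenario.

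| Severity odds ratio | Power, Chi-square | Power, CMH |
|---|---|---|
| 1 | 83.5–83.7% | 83.6–83.8% |
| 0.5 | 83.8–83.9% | 84.2–84.4% |
| 0.25 | 84.1–84.5% | 85.1–85.9% |
| 0.1 | 84.9–86.2% | 86.6–89.4% |

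Size over these scenarios is 5.8–6.9% for Chi-square and 6.8–7.9% for CMH.

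**4. Other assumed rates** (strata 50:50, moderate/severe):

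| Control v MSC | Overall | Power, Chi-square v CMH | Size, Chi-square v CMH |
|---|---|---|---|
| 17/3% v 50/20% | 10% v 35% | 84.6% v 85.9% | 6.4% v 7.7% |
| 45/15% v 72/38% | 30% v 55% | 72.0% v 74.1% | 6.0% v 7.8% |
| 60/10% v 85/35% | 35% v 60% | 73.5% v 81.0% | 4.1% v 7.6% |

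The last row needs a control severity odds ratio of (0.60/0.40)/(0.10/0.90) = 13.5 and a control rate of 35%, not 10%.

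**5. Paired test with no MSC effect.** One arm of 30, assumed baseline category 4 or 5, those still in hospital at day 28 spread over categories 2 to 5, signed-rank test at two-sided 5%. Probability of declaring improvement:

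| Discharged / dead by day 28 | Probability |
|---|---|
| 50% / 30% | about 94% |
| 30% / 30% | about 72% |
| 30% / 40% | about 45% |
| 40% / 50% | about 44% |
| 30% / 50% | about 22% |
| 10% / 50% | about 3% |

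The result follows the natural course of the disease, whatever MSC does.

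**The case against.** Much of the case for leaving the plan alone is sound. The Chi-square is the test on which the sample size was based, it is valid, and at the planned rates a stratified test adds only 0 to 3 points. Only about 30×0.10 + 30×0.35 = 13.5 responders are expected, so CMH strata would be sparse, and its size reached 7.9% in one scenario. Severity adjustment is planned, although only as exploratory. The paired tests are labelled exploratory too, and no confirmatory claim rests on them. Oxygen saturation and FiO2 are not listed endpoints in section 2.3.

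Four stronger readings are tempting, and the documents do not support them.

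- A reader might infer that ignoring the strata makes the primary test invalid or raises false positives. It does the reverse.
- A reader might expect a power loss of 7 points or more. That needs recovery rates and a severity effect far from section 8.2.
- A reader might infer that the paired tests would almost surely show improvement in the MSC arm. That holds only with favourable assumed outcomes; sections 1.1 and 1.3 cite ARDS mortality of up to or near 50%, where the probability is far lower. Nor does the text say that the tests are run within each arm. They could be pooled, which would not compare the arms either.
- A reader might infer that there is no between-arm analysis of these measures. The scale is compared between arms as a dichotomy at day 28, and the two-sample sentence may have been meant to cover the rest. Its place in the laboratory and imaging paragraph leaves that unclear.

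What remains is that the stratification factor is unused in the primary test, and that the paired tests do not address the study's question. The exploratory label does not cure the second.

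**Conclusion.** The point holds as a modest one in two parts. First, the primary test does not match the stratified randomization. It is conservative, with size about 4–7% against 7.5%, and costs about 0–3 points of power at 10% v 35%. The cost is larger only if severity is very strongly prognostic and control recovery is well above 10%. These ranges rest on assumed strata shares and severity effects. Second, the paired tests cannot inform MSC v control, and on their own they can be significant from natural recovery, in about 3% to 94% of arms of 30 under the assumed outcomes. This second conclusion follows from what a paired test compares and does not depend on those figures. The validity of the primary conclusion is not in question.

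**What to change.** - In section 8.5, make the primary day-14 test a CMH test stratified by ARDS severity as recorded at randomization, state the one-sided 7.5% level there, and report a stratified risk difference with its confidence interval. Update the named test in section 8.2 to match.
- For the six-point scale at days 14 and 28, add a between-arm ordinal analysis: a van Elteren test stratified by severity, or a proportional-odds model with severity stratum and baseline category. Death and discharge are already categories of the scale.
- For oxygen saturation and FiO2, use a baseline-adjusted comparison between arms where they are measured, and state how deaths and discharges are handled.
- Keep day-28 SOFA and CURB-65 descriptive. Under sections 6.1 and 7.2 they are taken then only in patients still in the ICU with a blood gas available, so a baseline-adjusted comparison would be made in a subset selected after randomization.
- State which measures the two-sample sentence covers. If paired tests are kept, say that they describe change and do not compare treatments.

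The stratum and the scale are already collected, so the cost is mainly wording in sections 8.2 and 8.5. The small statistical cost is sparse strata with about 14 expected responders and a size of up to about 7.9%.

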## 1 Background and Rationale

### 1.1 Acute Respiratory Distress Syndrome (ARDS)

Acute respiratory distress syndrome (ARDS) is an acute, life-threatening form of respiratory failure caused by diffuse inflammatory mediated alveolar injury leading to impaired gas-exchange, decreased compliance and fluid accumulation in the airspaces. Excessive inflammation is a major contributor to lung injury in ARDS leading to activation of the complement system by alveolar macrophages and the release of pro-inflammatory cytokines such as TNF, IL-1, IL-6, and IL-17, as well as multiple chemokines such as IL-8, CCL-2, and CCL-7 [1]. This leads to the accumulation of neutrophils and monocytes to the site of injury where they release toxic substances that damage the capillary endothelium and alveolar epithelium [1]. The ensuing cytokine storm leads to systemic inflammatory response, septic shock, and multi-organ failure [2, 3]. Multiple etiologies may trigger ARDS, including respiratory infections, sepsis/shock, trauma, pancreatitis, smoke inhalation, hematopoietic stem cell transplant, and transfusion-related acute lung injury.

ARDS is currently diagnosed based on the Berlin Definition of ARDS published in 2012 based on expert consensus [4]. It is clinically manifested by dyspnea and poor arterial oxygenation which is determined by the ratio of arterial partial pressure of oxygen to fraction of inspired oxygen ( $\text{PaO}_2/\text{FIO}_2$ ), along with bilateral opacities on chest imaging. ARDS is divided into 3 groups based on the degree of hypoxemia: mild ( $\text{PaO}_2/\text{FIO}_2$  201-300 mm Hg), moderate ( $\text{PaO}_2/\text{FIO}_2$ : 101-200 mm Hg), and severe ( $\text{PaO}_2/\text{FIO}_2 \leq 100$  mm Hg) and ventilator settings with a positive end-expiratory pressure (PEEP) or continuous positive airway pressure (CPAP)  $\geq 5$  cm  $\text{H}_2\text{O}$ . The mortality rate has been reported to be up to 50%, with increasing severity of ARDS leading to higher likelihood of mortality [5]. To date, no pharmacologic therapies have shown any benefit in reducing the high mortality of ARDS, and the primary treatment relies on treating underlying causes and supportive measures such as mechanical ventilation and fluid management [1]. Thus, effective therapies are needed.

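### The exploratory survival log-rank test names no strata although randomization is stratified by ARDS severity; to the extent that severity predicts death, it is somewhat conservative.

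*Combined protocol and SAP*

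**What the plan says.** Section 8.3 of the combined protocol and SAP states: "Randomization will be stratified by severity of ARDS (moderate and severe), and employ permuted blocks method". Section 5.2 says the same. Allocation is 1:1, and Section 8.2 gives "6 patients for safety run in and additional 30 patients in each treatment arm by randomization", so 60 patients are randomized.

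Section 1.1 describes ARDS mortality "with increasing severity of ARDS leading to higher likelihood of mortality". It gives a direction but no hazard ratio or rates by severity.

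"Overall survival" is a secondary endpoint in Section 2.3.2. Section 8.5 defines it: "Duration of overall survival will be days from date of randomization to date of death or date of last follow-up for censoring". The arms are described by Kaplan-Meier curves with medians and confidence intervals, then "compared with a log-rank test (comparison is considered exploratory"). No strata are named and no hazard ratio is planned. No significance level, event count or power is given for survival. Severity enters only an exploratory logistic regression of clinical improvement, which does not touch survival.

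**The concern.** When a prognostic factor is balanced between arms by design, part of the chance variation in the treatment comparison disappears. A log-rank test that ignores the factor still counts that part in its variance, so its p-values tend to be too large. Pooling strata with different hazards also dilutes the treatment contrast.

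At stake is the calibration and sensitivity of the one between-arm test planned for a named secondary endpoint, in a trial where few deaths can be expected. Changing the day-14 Chi-square test to respect the strata would leave this test as it is.

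**Working it through.** **The plan's own figure.** None exists for the log-rank test. The only stated power, 84%, belongs to the day-14 Chi-square test (10% vs 35%, 30 and 36 patients, one-sided 7.5%). Pooled rate = (3 + 12.6)/66 = 0.236. Standard errors are 0.1050 under the null and 0.0965 under the alternative. Power = Φ[(0.25 − 1.440 × 0.1050)/0.0965] = 84.7%. It reproduces, and the choice of survival test does not affect it.

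**Inputs from the documents.** 60 randomized patients, 1:1, two strata, survival timed from randomization, follow-up to day 28 (7.3).

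**Assumptions.** Exponential survival within each stratum, exact 1:1 balance within stratum, censoring at day 28, and the mortality rates, hazard ratios and stratum sizes shown below.

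**Statistics.** At each death, p is the MSC share of those at risk and g is 1 if the death is in the MSC arm, otherwise 0. U = Σ(g − p) and V = Σp(1 − p). The unstratified test uses z = U/√V over all 60 patients. The stratified test computes U and V within each stratum and uses z = (U₁ + U₂)/√(V₁ + V₂).

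**Implied severity hazard ratios.** With 28-day mortality m, the hazard is proportional to −ln(1 − m):
- 30%/50%: 0.693/0.357 = 1.9
- 30%/60%: 0.916/0.357 = 2.6
- 25%/65%: 1.050/0.288 = 3.6

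**Result 1.** One-sided 2.5%, treatment hazard ratio 0.4 for power, 400,000 simulated trials per cell. The simulation standard error is about 0.03 points for null rejection and 0.08 points for power.

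| Control mortality, moderate/severe | Patients, moderate/severe | Null rejection, unstratified vs stratified | Power, unstratified vs stratified |
|---|---|---|---|
| 30%/50% | 30/30 | 2.3% vs 2.6% | 44.8% vs 46.0% |
| 30%/60% | 30/30 | 2.0% vs 2.6% | 48.2% vs 51.3% |
| 25%/65% | 30/30 | 1.6% vs 2.6% | 46.2% vs 52.1% |
| 30%/50% | 50/10 | 2.4% vs 2.5% | 38.0% vs 38.6% |
| 30%/50% | 10/50 | 2.4% vs 2.6% | 51.9% vs 52.5% |

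Smaller runs put the unstratified null rate in the first row anywhere from 2.2% to 2.4%. The power gains in the first three rows are 1.2, 3.1 and 5.9 points. They shrink to 0.6 points when one stratum holds only 10 patients.

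Expected deaths at hazard ratio 0.4, first row: MSC mortality is 1 − 0.7^0.4 = 13.3% and 1 − 0.5^0.4 = 24.2%. With 15 patients per arm per stratum, deaths = 15 × (0.30 + 0.50 + 0.133 + 0.242) = 17.6.

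**Result 2.** Two-sided 5%, treatment hazard ratio 0.5 for power, overall control mortality 50% (the level cited in Section 1.3), half of patients severe, 100,000 trials per cell.

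| Severity hazard ratio | Type I error, unstratified vs stratified | Power, unstratified vs stratified |
|---|---|---|
| 1 | 5.0% vs 5.0% | 38.6% vs 38.5% |
| 1.5 | 4.9% vs 5.1% | 38.3% vs 38.8% |
| 2 | 4.5% vs 5.2% | 36.5% vs 38.4% |
| 3 | 3.5% vs 5.2% | 34.2% vs 39.2% |
| 4 | 2.9% vs 5.3% | 31.5% vs 39.7% |

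With control mortality of 35%, the gain is 1.2 points at a severity hazard ratio of 2 and 2.7 points at 3.

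**The case against.** The plan labels this comparison exploratory, gives it no significance level or power, and rests no decision on it. An unstratified log-rank test is valid, and it matches Kaplan-Meier curves drawn by arm. The size of the effect depends on how prognostic severity is, which the documents do not say. An even split between strata is also close to the most favorable case for stratifying. Power is low with either test: at a hazard ratio of 0.6 with 30%/50% mortality and an even split, it is 19.1% unstratified and 20.2% stratified. Ignoring the strata matters more for the primary Chi-square test.

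All of this stands, and it keeps the point minor. It does not remove it. The p-value will still be reported for a named secondary endpoint, and stratifying loses only about 0.1 point of power when severity is unrelated to death.

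A reader might go further in three ways that the documents do not support:
- **That the unstratified test always loses power.** Section 1.1 gives a direction and no size, and at a severity hazard ratio of 1 to 1.5 the loss is nil or about half a point.
- **That the planned test gives false positives or undermines the trial's conclusions.** Its error is on the conservative side, and the 84% power concerns another endpoint.
- **That the plan deliberately rules out stratification.** Section 8.5 is silent. The unstratified test is the ordinary reading of an unqualified log-rank test, not a stated choice.

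**Conclusion.** The point holds as a small, conditional improvement. If severity predicts death with a hazard ratio of about 2 to 3.6, and the strata are of similar size, the unstratified test rejects about 2.3% down to 1.6% of the time under the null (nominal 2.5%). It then gives up about 1 to 6 points of power at a treatment hazard ratio of 0.4. If severity is weakly prognostic, nothing material changes; if one stratum is small, the gain is about half a point. Stratifying brings the test into line with the randomization, but it does not turn survival into an adequately powered endpoint: power is near or below 50% at the mortality rates of Result 1, and 40% or less in Result 2.

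The mortality rates, hazard ratios, stratum sizes and exponential shape are all assumptions. Only the stratified design, the sample size, the follow-up and the direction of the severity effect come from the documents.

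**What to change.** In Section 8.5, compare overall survival with a log-rank test stratified by the ARDS severity stratum recorded at randomization. Report a hazard ratio with its confidence interval from a Cox model stratified the same way. Keep the comparison labelled exploratory; the unstratified test can be retained as a sensitivity analysis.

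Section 3.1 places a PaO2/FiO2 of exactly 100 in both the moderate and the severe group, whereas Section 1.1 starts moderate at 101. These definitions should be reconciled. Analyzing by the stratum recorded at randomization avoids reclassifying patients afterwards.

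The cost is a sentence or two in Section 8.5, with no new data or patients. There are two small downsides. The hazard ratio becomes conditional on stratum, which the report should say. The stratified test can also run slightly above nominal: about 0.1 point at one-sided 2.5%, and 0.1 to 0.3 points at two-sided 5% for severity hazard ratios of 1.5 to 4.

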### **2.3.3 Exploratory endpoints**

1. Changes in inflammatory markers (CRP, IL-6, IL-10, TNF- $\alpha$ )
2. Negative SARS-CoV-2 RT-PCR by day 28 (if available)
3. Changes in blood safety laboratories (CBC with differential, electrolytes, renal indices, liver function studies, LDH, coagulation studies if available)
4. Corticosteroid use and duration
5. Changes in chest imaging
6. Evolution of other end-organ damage (hepatic, renal, cardiovascular)
7. Changes in disease severity score (SOFA, CURB-65)
8. Duration of vasopressor use

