# - if inadequate response to initial infusion, a second infusion may be given within 3-5 days following the first infusion; no more than 2 infusions will be administered

@ - coagulation studies = PT/aPTT, d-dimer, fibrinogen

& - collected pre-infusion and 3-4 hours post-infusion

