### 7.1 Baseline Pre-treatment Evaluation

- 7.1.1 History and physical (including vitals and oxygenation requirements)
- 7.1.2 SARS-CoV-2 RT-PCR testing
- 7.1.3 ARDS assessment
- 7.1.4 Complete Blood Count and differential (CBC)
- 7.1.5 Complete Metabolic Panel (CMP)
- 7.1.6 Coagulation studies: PT/aPTT, d-dimer, fibrinogen
- 7.1.7 Lactate Dehydrogenase (LDH)
- 7.1.8 C-Reactive Protein (CRP)
- 7.1.9 CXR and/or CT chest imaging
- 7.1.10 Urine or serum pregnancy test for females of childbearing potential
- 7.1.11 APACHE II score
- 7.1.12 Medical record review for concomitant medications
- 7.1.13 Clinical status assessed by the six-category ordinal scale (1 = discharged; 6 = death)

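### Section 8.5 compares laboratory and inflammatory markers between arms with two-sample tests that adjust for neither the baseline value nor ARDS severity, losing precision in an exploratory comparison

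*Combined protocol and SAP*

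**What the plan says.** Section 2.3.3 lists "Changes in inflammatory markers" (CRP, IL-6, IL-10 and TNF-alpha) as the first of eight exploratory endpoints. Section 8.5 says of laboratory data, including these markers: "Changes from baseline to post-treatment will be plotted for each patient over time and assessed using paired test methodologies when appropriate". The next sentence gives the between-arm method: "Comparison between the two treatment groups will be exploratory with appropriate two-sample tests". It does not state what quantity enters the test, and it names no covariate. The only adjusted model in Section 8.5 is an exploratory logistic regression for clinical improvement.

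Section 7.1 puts CBC, CMP, coagulation studies, LDH and CRP in the pre-treatment evaluation. The research cytokines are not on that list. Their first sample is on day 0, which a footnote to the Section 6.1 calendar describes as "collected pre-infusion and 3-4 hours post-infusion". Section 7 defines day 0 as the day of infusion in the MSC arm and the day of randomisation in the control arm. Sections 5.2 and 8.3 stratify randomisation by ARDS severity.

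**The concern.** A test of the post-treatment value discards the baseline. A test of the change subtracts it in full, which over-corrects when baseline and follow-up are only moderately correlated. Both leave the estimate exposed to chance baseline differences, and neither uses the stratification factor. The primary hypothesis in Section 2.2.1 concerns the inflammatory response, and these markers are the most direct evidence on it. With at most 30 patients per arm, a chance imbalance in baseline CRP or IL-6 could produce or conceal an apparent effect. Leaving the choice between value and change open also allows it to be made after the data are seen.

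**Working it through.** **The plan's own figure.** No power is stated for any marker. The only power figure is 84% for the primary endpoint in Section 8.2 (10% v 35%, 30 control v 36 MSC, one-sided 7.5%, Chi-square). It reproduces:

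- Pooled rate = (30 × 0.10 + 36 × 0.35)/66 = 0.236; null SE = 0.1050; alternative SE = 0.0965; z = 1.4395.
- Power = Φ[(0.25 − 1.4395 × 0.1050)/0.0965] = 84.7%.

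That figure says nothing about the markers, so what follows rests on assumptions.

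**Inputs.** From the documents: n = 30 per arm (Section 8.2: "6 patients for safety run in and additional 30 patients in each treatment arm by randomization"), allocated 1:1. Assumed: two-sided 5%; equal SDs; a standardised effect d of 0.6 or 0.736 (the latter, about 0.74, gives 80% power on final values); and a baseline-to-follow-up correlation ρ of 0.3 to 0.8.

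**Residual variance, in units of the marker variance.**

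- Final value: 1
- Change: 2(1 − ρ)
- ANCOVA on baseline: 1 − ρ²

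ANCOVA is lower than final value by ρ² and lower than change by 2(1 − ρ) − (1 − ρ²) = (1 − ρ)². The direction of the gain for 0 < ρ < 1 therefore does not depend on how Section 8.5 is read, apart from the cost of one degree of freedom. At ρ = 0.5 the reduction is 25% against either test.

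**Power.** Noncentral t with noncentrality d × √(n/2)/√(residual variance), on 58 df (57 for ANCOVA). For d = 0.6 on final values this is 0.6 × √15 = 2.324. For ANCOVA at ρ = 0.5 it is 2.324/√0.75 = 2.683.

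| d | ρ | Final value | Change | ANCOVA |
|---|---|---|---|---|
| 0.6 | 0.3 | 62.8% | 48.9% | 66.8% |
| 0.6 | 0.5 | 62.8% | 62.8% | 75.1% |
| 0.6 | 0.7 | 62.8% | 83.9% | 89.2% |
| 0.736 | 0.3 | 80.0% | 65.9% | 83.6% |
| 0.736 | 0.5 | 80.0% | 80.0% | 89.9% |
| 0.736 | 0.7 | 80.0% | 95.1% | 97.5% |
| 0.736 | 0.8 | 80.0% | 99.3% | 99.7% |

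At d = 0.736 the gain over final value runs from 3.6 points (ρ = 0.3) to 19.7 (ρ = 0.8). The gain over change runs from 17.7 down to 0.4. ARDS severity is not in this calculation; its contribution cannot be sized from the documents.

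**Fewer patients with values.** The same formula at d = 0.736 and ρ = 0.5 gives 62.1% (final value) to 74.4% (ANCOVA) at 20 v 20, and 49.5% to 61.2% at 15 v 15. Those are gains of 12.3 and 11.7 points.

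**Chance imbalance.** With 30 v 30 the SE of the baseline difference is √(2/30) = 0.26 SD. For an observed imbalance of that size, the final-value difference shifts by ρ × 0.26 and the change difference by −(1 − ρ) × 0.26. At ρ = 0.5 that is 0.13 SD either way, against an assumed effect of 0.6 SD. ANCOVA removes this shift, apart from error in estimating the slope.

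**The case against.** The strongest reply is that the comparison is expressly exploratory, that no stated power or decision rule depends on it, and that under randomisation a two-sample test of either quantity is valid. All of that stands.

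A reader might infer that the plan ignores baseline altogether. The text does not support this: the endpoint is worded as changes, and the preceding sentence of Section 8.5 concerns changes from baseline, so a two-sample test of change is a natural reading. If ρ is 0.7 or more, the loss on that reading can be small.

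A reader might also infer that about 10 points of power are lost. That figure arises at ρ near 0.5 with reference power about 80% and two-sided 5%, none of which the plan states for the markers. At one-sided 7.5%, the only alpha in the plan and set for the primary endpoint, the 0.74 SD, ρ = 0.5 case goes from 91.9% to 96.7%, a gain under 5 points.

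Nor does every marker have a baseline defined alike in both arms. The only pre-treatment cytokine sample is tied to an infusion that controls do not receive. The opposite inference, that controls have no cytokine baseline, also goes too far: Section 7 gives them a day 0 and the same evaluation schedule. Only the clock time is missing.

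Finally, 30 v 30 is an upper bound. Post-baseline CRP, LDH and coagulation values are taken only if routine care produced them (Section 7.2.3), and cytokines at days 14 and 28 are required only while the patient is in hospital. ANCOVA on available values does not remove selection arising from that.

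**Conclusion.** The point holds as an efficiency recommendation of low severity. Section 8.5 leaves the tested quantity open and adjusts for neither the baseline value nor the stratum, although both are collected. Reading this as a validity error would be wrong: the planned tests are unbiased over randomisation, and the weakness is lower precision and exposure to imbalance in the one sample observed.

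Under the assumptions of 30 v 30, two-sided 5% and 0.6 SD, ANCOVA gains about 4, 12 and 26 points over final values at ρ = 0.3, 0.5 and 0.7, and about 18, 12 and 5 points over change scores. At about 0.74 SD and ρ = 0.7 the gain over change is about 2 points. No single figure should be quoted as the cost of the plan.

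**What to change.** In Section 8.5, replace the two-sample tests for continuous laboratory and inflammatory markers with one of the following, keeping the exploratory label:

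- ANCOVA of the post-treatment value at one named scheduled day. Day 7 is an example: in the calendar it is the last cytokine sample not marked as conditional on remaining in hospital.
- A repeated-measures model over the scheduled days.

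In either case:

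- Include treatment, the baseline value of the marker and ARDS severity (moderate or severe) as covariates.
- Analyse CRP and the cytokines on the log scale.
- Include randomised patients with values, and report the number contributing in each arm.
- Report the adjusted ratio or difference with its 95% confidence interval.
- For cytokines, define baseline as the pre-infusion day 0 sample in the MSC arm and the day 0 (day of randomisation) sample in controls, and state that timing in Section 7.2.6 and the calendar footnote.

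The cost is wording in Section 8.5 and one clarifying line on control-arm cytokine sampling. No added patients or visits are needed.
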